5.2 Efficacy Evaluations

5.2.1 Diagnostic Tests, Scales, Measures, etc.

Movement Data Processing: The first step in the processing chain is to apply calibrations and filters to correct intrinsic errors (e.g. sensor bias, scale factor, non-linearity) and extrinsic errors (e.g. sensor mounting, movement artifacts, external magnetic fields). This will be done using an Error-State Extended Kalman Filter (EKF) fusing the accelerometer, gyroscope, magnetometer, and a physical motion model together in a statistically valid fashion. Anomalous movements well outside of the expected range (e.g. a player bumping the sensor) are flagged by the sensor to avoid corrupting data interpretation. The filtered sensor data is then used to estimate time-series quantities such as short-time window 3-D motion paths, orientation stability, velocity vectors, and tangential and centripetal accelerations.

Movement Classification: The system is only interested in analyzing a subset of the movements executed during play hence the next step in the processing chain is detection / classification of movements of interest. This process begins with separation of processed time-series data into portions containing movements of unknown type. This is done with a classifier trained to discriminate fixed sized windows into either start of movement, end of movement, or other classes. This separation process is important as different actions will on average take differing amounts of time. Attempting to classify actions directly with fixed window sizes results in diminished discriminative power as the timeseries values used to produce these features will likely be taken from a period where the system is in multiple states [39], [40]. After action segmentation, a secondary feature set will be calculated over the movement timeseries and used to classify the movement to a known class of actions in the given sport (e.g. forehand swing, backhand swing, serve in tennis). IDL has had success with the decision tree classifier in previous efforts and will begin our research efforts with this algorithm. The tree is trained offline using the C4.5 algorithm with data acquired in the research facility [41]. The resulting decision trees are then used for real-time classification on the sensor hardware.

Movement Phase Segmentation: After detection and classification, movements are further segmented into constituent phases. The true phase of the movement is modeled as a hidden Markov model where time series data or windowed feature data derived from the time series data are used as emissions of the Markov process. Using the set of emissions recorded, the optimal set of series of states is calculated using the Viterbi algorithm [2]. Emissions distributions for the phases of a movement are determined from truth data gathered in the Epic Sports Biomechanics research facility.

Biomechanical interpretations: Pseudo Biomechanical Variables (PBVs) related to the true biomechanical values such as torques on joints and forces applied to ligaments are estimated at the final stage in the processing pipeline. This is accomplished using a combination regression analysis and a phase-specific simplified inverse biomechanical model. Since movement phases are associated with specific biomechanical configuration and displacements of the body segments within a phase are constrained by design, the inverse mapping is determined over a smaller problem subspace. Regression analysis is used offline to calculate a mapping between biomechanical values of interest (e.g. torque in shoulder) and sensor measurements (e.g. x dimension acceleration). The regression is simplified through use of the least absolute shrinkage and selection operator (LASSO) to determine the

minimum set of active joint variables to improve computational performance when executed on sensor hardware in real-time [42].

These values are then used to determine the probability of injury as well as calculate performance estimates such as pitch velocity. PBVs are also paired with movement phase information, stored, and available for viewing by the player, parents, and coaches to aid in quick identification of problems with form or opportunities to improve performance. Injury estimation cost functions will score actions based on the potential for accumulated overuse injury risk. For example, large forces on the UCL during the stride phase of a baseball pitch due to an excessive rotation of the forearm from the horizon to the vertical plane would accumulate a higher cost than a similar pitch with proper form [43].

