6.3 Statistical Methods

6.3.1 Baseline Data

Data will be analyzed with the goal of determining the feasibility of the approach. The accuracy of movement classification, movement phase segmentation, mapping of sensor reading to biomechanical values, and movement detection will all be quantified. K-fold cross validation will be used to estimate the performance of regressors and classifiers. Regressor performance will be quantified via the mean and standard deviation of error values between predicted biomechanical variable values and actual values as determined from motion capture data. Biomechanical value prediction models will be considered successful if error distributions have mean and standard deviation of less than 5% and 10% respectively of the nominal value. Sensitivity and specificity will be used to quantify the

performance of movement detection and classification algorithms. Movement segment detection will be considered correct if the algorithm identifies 90% of time occupied by the movement. Detection algorithms will be considered successful if they are able to operate with specificity and sensitivity of 95%.

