8.5 Recruitment Strategy

Participants for the Pilot Phase will be recruited from orthopaedics physical therapy clinics at CHOP. Potential subjects will be identified by a member of the study team based on screening sports medicine physical therapy clinic schedules against the inclusion/exclusion criteria. Patients who are qualified for the study (based on the inclusion/exclusion criteria) will be approached and consented during their physical therapy visit.

Participants for Phase 1 will be recruited from multiple sources including solicitation letters sent to local youth sport organizations, fliers placed in the Sports Medicine Centers throughout CHOP organization, and or personal solicitation via email, phone, or in-person contact. Patients who are qualified for the study (based on inclusion/exclusion criteria) and who respond to solicitation or other recruitment strategies will be consented via e-consent processes using REDCap and will have the opportunity to ask questions during a phone call with a member of the study team prior to signing the eConsent. At the biomechanics laboratory for throwing performance housed at Epics Sports Biomechanics, the subjects will undergo additional data collection within the 3-D motion laboratory in order to augment training data and re-estimate the accuracy of the various algorithmic components.

For the Pilot Phase, a convenience sample of 20 youth athletes will be recruited to participate. Recruitment will stop when 10 evaluable subjects have undergone data collection.

For Phase 1, a convenience sample of 20 youth baseball pitchers, will be recruited to participate in this study. Recruitment will stop when 10 evaluable subjects have undergone data collection.

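### Section 6.3.1 judges success by plain K-fold in the children used for development, with no selection rule, nesting or held-out children, so the 95% and 10% SD verdicts may be optimistic

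*Combined protocol and SAP*

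**What the plan says.** The combined protocol and SAP describes a chain of fitted components in section 5.2.1.

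- **Classifier.** A C4.5 decision tree, trained on research-facility data, is the starting point: "IDL has had success with the decision tree classifier in previous efforts and will begin our research efforts with this algorithm". No other candidate is listed, and there is no rule for keeping or replacing the tree.
- **Phase model.** "Emissions distributions for the phases of a movement are determined from truth data gathered in the Epic Sports Biomechanics research facility".
- **Load regression.** "The regression is simplified through use of the least absolute shrinkage and selection operator (LASSO) to determine the" smallest set of joint variables that can be run in real time on the sensor. No rule for the penalty is given.

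Section 3.1 makes creating and refining the algorithm the goal of Phase 1, with 10 evaluable children. Section 8.5 has these children provide laboratory data "in order to augment training data and re-estimate the accuracy of the various algorithmic components".

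On evaluation, section 6.3.1 states "K-fold cross validation will be used to estimate the performance of regressors and classifiers". It then sets pass limits. The error mean must be below 5% and the error SD below 10% of nominal, and "Detection algorithms will be considered successful if they are able to operate with specificity and sensitivity of 95"%. The number of folds, the unit that is folded, nesting and any held-out set are not stated.

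**The concern.** Cross-validation gives an honest error estimate for a procedure only if every data-driven step of that procedure is repeated within each training fold. If the features, the penalty or the algorithm itself are chosen on all Phase 1 children, or by comparing the fold errors that are later reported, the left-out child has already influenced the model. The reported figure is then partly the best of several tries. Keeping all of one child's pitches in the same fold solves a different problem and does not remove this one.

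At stake are the pass/fail statements on detection and load estimation. Under section 5.2.1 the load estimates feed an injury probability and can be viewed by players, parents and coaches. Section 9 plans publications and possible use in grant applications. An algorithm that misses a limit could be reported as having met it.

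**Working it through.** **1. The plan's own figures.** Section 6.4 enrols 2 × (10 evaluable + 10 extra) = 40, which reproduces. It has no bearing on this point. The 95%, 5% and 10% limits are given without derivation, so there is nothing further to reproduce.

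**2. Development and evaluation side by side.** The tree and the phase model are trained on research-facility data (5.2.1). The regression targets come from motion capture at the same facility (6.3.1, 6.3.2). Accuracy is re-estimated from the same children (8.5). The Pilot Phase uses other children without motion capture and is not offered as a test set. Training and judgement of the final models therefore share 10 children.

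**3. Choosing among algorithms.** Documents: 10 children and 30-45 pitches each (38 used). Assumed: every candidate has true sensitivity 0.93, within-child correlation r is 0.02 or 0.10, correlation between candidates is 0.5 or 0.8, and the normal approximation holds.

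SE = √[0.93 × 0.07 / 380 × (1 + 37r)]

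- r = 0.02: SE = 0.0173; z = 0.02/0.0173 = 1.16; chance of observing at least 95% = 12%.
- r = 0.10: SE = 0.0284; z = 0.02/0.0284 = 0.70; chance = 24%.

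Keeping the best of several candidates on the same folds (20,000 draws per setting):

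| r | One fixed | Best of 5 (candidate correlation 0.8 / 0.5) | Best of 10 (0.8 / 0.5) |
|---|---|---|---|
| 0.02 | 12% | 24% / 35% | 31% / 46% |
| 0.10 | 24% | 42% / 55% | 49% / 68% |

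For true sensitivity of 0.92 to 0.94, the mean optimism for the best of 5 is 0.8 to 2.5 percentage points. With one algorithm fixed in advance it is zero.

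The rule also requires specificity. If specificity is 93% too, with equal and independent variance, a fixed algorithm passes both with probability 0.123² = 1.5% to 0.240² = 5.8%. With r from 0.05 to 0.2, the joint pass rate is 3-9% for one fixed algorithm and 12-40% for the best of 10. The absolute rates fall; the relative inflation remains.

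**4. Penalty tuning alone.** Assumed: 30 features, leave-one-child-out folds, 200 simulated studies per setting, two settings for the split of error between and within children. SDs are in % of nominal.

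| Setting | Same-fold SD | Nested SD | True SD, new children | Reported SD below 10%: same-fold / nested |
|---|---|---|---|---|
| A | 10.08 | 10.56 | 10.43 | 48% / 40% |
| B | 9.88 | 10.16 | 9.95 | 62% / 48% |

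Same-fold optimism is 10.43 − 10.08 = 0.35 and 9.95 − 9.88 = 0.07 points. Nesting errs slightly the other way, by 0.13 and 0.21 points.

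**5. Feature selection outside the folds.** Assumed: 200 features screened to 20 on all data, then LASSO. The reported SD is 8.8 against a true 10.8. The 10% limit is passed in 96% of studies, while 2.5% truly meet it. Nesting only the penalty does not repair this (8.9; 93% pass).

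A second design assumes that children's mean loads differ by an SD of 15% of nominal, that the features carry no information on that difference, and that 3 are kept. The pass rate with selection outside against inside the folds is 15% against 4% (15 features), 26-28% against 6% (30) and 39% against 7% (60).

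**6. The 5% mean-error limit.** In the LASSO runs of steps 4 and 5, the reported mean error met it in 100% of studies. In new children 94-99.5% also met it. Selection hardly moves this verdict.

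**The case against.** A reader might infer that the algorithm, features and penalty are in fact chosen on the reported folds. No section says so. Section 5.2.1 names one classifier and says the resulting trees go onto the sensor. If C4.5 and LASSO are refitted in each training fold with nothing chosen outside, their internal selection causes no optimism. This objection stands: the plan is silent, and the optimism is a risk, not an established fact.

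The larger figures also depend on invented inputs. Five or ten equally good candidates are an assumption. Section 5.2.1 describes no correlation screening before LASSO, and it combines the regression with a phase-specific biomechanical model that was not simulated. In the second feature design the median apparent SDs (14.8%, 12.5% and 11.0% for 15, 30 and 60 features) still miss the 10% limit. These points limit the size, not the direction.

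A reader might also take these verdicts to be the only quantitative conclusions about the device. They are not: section 6.3.1 also quantifies classification and phase segmentation, and the Pilot Phase validates basic measurements. Sections 6.3.1 and 6.4 call the work feasibility and exploratory. That lowers the stakes but does not remove the problem, because explicit success limits are still set.

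Finally, nesting has limits. It does not cure the 12-24% pass rate of a fixed algorithm with true sensitivity 93%, which comes from judging a point estimate. Nor can an inner loop replay manual refinement of hardware and firmware.

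**Conclusion.** The point holds as a gap in the evaluation plan. Plain K-fold in the development children, with no selection rule, nesting, locked pipeline or held-out children, does not protect the 95% and 10% SD verdicts from selection optimism. Child-level folds alone would not do so either.

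The direction is clear if any selection happens outside the training folds; whether it will is not stated. Under the stated assumptions the effect is small for penalty tuning, moderate for choice among several algorithms, and potentially large for feature selection on all data. The documents supply none of the correlations, candidate counts or feature counts behind these sizes. The 5% mean-error limit should not be counted among the exposed verdicts. A change is worth making because it is cheap and bears directly on the stated success rules.

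**What to change.** In section 6.3.1, replace plain K-fold with nested cross-validation.

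- **Outer loop:** leave one child out.
- **Inner loop, remaining children only:** repeat every automated data-driven step, namely window and feature selection, LASSO penalty and active set, tree pruning, and choice among a closed list of candidate algorithms written down beforehand. The Markov states need no tuning if they are the movement phases that the biomechanist labels; their emission distributions should be fitted on training children only.
- **Decision:** apply the 95% and 10% SD limits once, to the outer-loop predictions.
- **Reporting:** give the number of variants tried, and label any result from manual or same-fold refinement as development performance.

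The cost is a wording change, more computing time, a candidate list fixed in advance, and reported accuracy that will be somewhat less favourable. No extra children or visits are needed. If the team already intends to keep all selection inside the training folds, stating that and the candidate list closes most of the gap.

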5.3 Safety Evaluation

This is a minimal risk study. The Principal Investigator will be responsible for monitoring the safety of study subjects and complying with all reporting requirements. Members of the study team who perform the motion analysis will monitor subjects throughout to ensure that they do so safely. The PI and study investigators will monitor data accuracy and identify ways to resolve any problem areas.

6 STATISTICAL CONSIDERATIONS

6.1 Primary Endpoint

- The primary endpoint of this study is to quantify motion capture data on movements common to baseball play.

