2.1 Primary Objective (or Aim)

The primary objective of this study is to collect motion-capture data on movements common to baseball play in order to develop a wearable device for the prevention and rehabilitation of sports-related overuse injuries.

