5.1.6 Phase 1 Throwing Evaluations

At the Epic Sports Biomechanics research facility, subjects will wear the throwing monitor device prototype during a simulated baseball game, pitching approximately 30-45 times using varying pitch types (fastball, change-up, etc.) as they would within a typical game. In addition, each player will perform a set of other baseball-specific movements (field-based overhand throw, run, bat swing, catch ball) typically seen in baseball play. Participants will be fitted with 51 infrared reflective markers to enable tracking of limb, torso, and head movement while actions are performed. Movement data will be video recorded and recorded with 12 Motion Analysis Raptor IR cameras encompassing a capture volume of 26ft length x 7ft width x 8ft height. A minimum of 3 time-synchronized video cameras placed at different viewing perspectives will also record participants as they perform movements. Subjects will be asked to return the throwing monitor device by the end of the study visit.

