6.3.2 Efficacy Analysis

Data recorded from the motion capture system will be analyzed with C-Motion Research Visual 3D v5 Professional and used to derive biomechanical variables of interest when performing movements associated with overuse injuries or of interest for performance monitoring. Analysis will calculate a time series of torques, compression forces, and tension forces on joints, ligaments, and muscles of interest. A biomechanist at the Epic Sports Biomechanics research facility familiar with baseball will review video of each movements of interest (e.g. pitches) and segment movements into their constituent phases. Additionally, the biomechanist will flag any abnormalities in data such as aborted movements and instances of improper form or technique.

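### The primary endpoint is a task on the reference system, and the device-accuracy criteria in section 6.3.1 are tied to no endpoint, no deciding variable and no athlete-level validation

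*Combined protocol and SAP*

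**What the plan says.** The primary endpoint in section 6.1 is a single sentence: "The primary endpoint of this study is to quantify motion capture data on movements common to baseball play". The primary objective in section 2.1 runs parallel to it: "The primary objective of this study is to collect motion-capture data on movements common to baseball play in order to develop a wearable device".

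Motion capture is the facility's camera system, not the wearable. Under section 5.1.6, movements are "recorded with 12 Motion Analysis Raptor IR cameras", with 51 reflective markers on the athlete. Section 6.3.2 gives the processing: "Data recorded from the motion capture system will be analyzed with C-Motion Research Visual 3D v5 Professional". The output is a set of torques, compression forces and tension forces on joints, ligaments and muscles of interest. No criterion is attached to it.

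The criteria for the device are in section 6.3.1, under the heading Baseline Data. Predictions from the sensor are compared with "actual values as determined from motion capture data", and "Biomechanical value prediction models will be considered successful if error distributions have mean and standard deviation of less than 5% and 10% respectively" of a nominal value. Detection algorithms need sensitivity and specificity of 95%. A movement segment counts as correctly detected if 90% of its time is identified. Performance is estimated by K-fold cross-validation.

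Section 6.2 lists algorithm development and, for the Pilot Phase, validation of basic device measurements as secondary endpoints. Neither has a metric. Section 3.1 calls the study a prospective reliability study. Section 6.4 calls it exploratory and gives no power analysis.

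**The concern.** A reader of a reliability study with stated feasibility aims will look to the primary result to learn whether the device agrees with the reference. As worded, that result concerns the reference system only. It is equally compatible with an accurate device and an inaccurate one.

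The informative criteria in section 6.3.1 have three gaps. First, they belong to no endpoint, so their rank is unknown. Second, they apply to prediction models in general, and nothing says which variable or variables must pass for the approach to be called successful. Third, K-fold without a splitting rule allows pitches from one athlete to fall in both the training and the test fold. The estimated error may then describe athletes the model has already seen, whereas the device is meant for new ones. At stake is a success claim that could be selective, optimistic or both. Section 9 foresees publication and use of the data in grant applications.

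**Working it through.** **1. Head count.** Section 6.4 plans 20 enrolled to give 10 evaluable in each phase. The implied loss is 50%: 10 / (1 − 0.5) = 20 per phase, and 2 × 20 = 40, which matches the stated total. Motion capture is described only for Phase 1 (sections 3.1.3, 4.2.2 and 5.1.6). The primary endpoint as worded, and any device-versus-motion-capture comparison, therefore rest on 10 evaluable athletes.

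**2. What each section supplies.**

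| Element | 6.1 Primary | 6.2 Secondary | 6.3.1 Baseline Data |
|---|---|---|---|
| Device quantity | none | device measurements, algorithms | predicted biomechanical values, detection |
| Named deciding variable | none | none | none |
| Summary | none | none | mean and SD of error; sensitivity, specificity |
| Threshold | none | none | 5% / 10%; 95%; 90% of time |
| Link to an endpoint | – | – | none stated |

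The thresholds and the endpoints never meet in one section.

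**3. What unspecified folds allow.** Sections 4.2.2 and 5.1.6 give about 30 to 45 pitches per athlete. If pitches are assigned to folds at random, a share (K − 1)/K of each athlete's pitches is expected in training whenever some of that athlete's pitches are being tested. K is not stated. For an assumed K = 5 this is 0.8 × 30 = 24 to 0.8 × 45 = 36 pitches. For K = 10 it is 0.9 × 30 = 27 to 0.9 × 45 = 40.5. Only splitting by athlete brings this to zero.

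**4. How much information 10 athletes give.** Total pitches: 10 × 30 = 300 to 10 × 45 = 450. With m pitches per athlete and within-athlete correlation r, the design effect is 1 + (m − 1)r, and the effective number is the total divided by it. The documents give no r, so the values below are assumptions. The half-width for a sensitivity of 95% is 1.96 × √(0.95 × 0.05 / n_eff). The half-width for the mean error, taking the error SD at its 10% limit, is 1.96 × 10 / √n_eff.

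| r | Design effect (m = 30; 45) | n_eff | Sensitivity ± (points) | Mean error ± (points) |
|---|---|---|---|---|
| 0 | 1; 1 | 300; 450 | 2.5; 2.0 | 1.1; 0.9 |
| 0.1 | 3.9; 5.4 | 76.9; 83.3 | 4.9; 4.7 | 2.2; 2.1 |
| 0.3 | 9.7; 14.2 | 30.9; 31.7 | 7.7; 7.6 | 3.5; 3.5 |

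At r = 0.3, for a 95% interval for the mean error to lie within ±5%, the observed mean would have to be within about 5 − 3.5 = 1.5 points of zero. With only 10 athletes, these normal-theory widths are on the narrow side.

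**The case against.** The strongest reply is that motion capture here is development material as well as the comparator. Sections 5.2.1 and 6.3.2 use the facility data to train the classifier, set the phase distributions and fit the regression. A primary endpoint about that dataset suits a primary objective of collecting it, and the study is declared exploratory. This stands, and it is why data collection should remain an aim. It does not supply the missing variable and summary, and section 6.4 uses the exploratory label only to explain the absence of a power analysis.

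A reader might infer that the endpoint is met as soon as anything is recorded. The documents do not support this: quantifying implies the Visual 3D processing and the biomechanist's review in section 6.3.2, and 10 evaluable athletes are planned. What is missing is a stated minimum amount or quality of data.

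A reader might also infer that one variable inside 5%/10% would make the study a success. No such rule exists. Section 6.3.1 says the several accuracies will all be quantified, and the limits read as applying to each model. The gap is that no rule is given in either direction. A chance of a lucky pass cannot be calculated, because the documents give neither the number of variables nor their pass probabilities, and variables from the same throws are unlikely to be independent.

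**Conclusion.** The point holds as one of definition and linkage. The primary endpoint has no variable, summary or threshold and cannot show whether the device works. The plan does assess the device in section 6.3.1, but without an endpoint, a deciding variable or a rule for splitting folds. It would be too strong to say that the plan ignores device accuracy, or that meeting the primary endpoint would count as a favourable device result: section 6.1 makes no claim about the device.

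No single number measures the defect. The precision figures above depend on assumed correlations of 0 to 0.3 and, for the mean error, on an SD at its limit. They show why an interval must allow for clustering; they do not predict the result. The conclusion on endpoint definition rests on the text alone. This should be corrected before analysis. The study is minimal risk, and the point raises no safety issue.

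**What to change.** Keep motion-capture data collection as the development aim, and state in section 6 a device-accuracy endpoint to which the section 6.3.1 criteria belong:

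- **Measure:** Phase 1 error between the device-predicted and the motion-capture value of one variable that the sponsor names before analysis. Shoulder torque appears in section 5.2.1 only as an example, so the choice is the sponsor's.
- **Validation:** K-fold with folds split by athlete, so that every prediction is for an athlete not used in training.
- **Scale:** define the nominal value that serves as denominator, and say that the mean-error limit refers to absolute size.
- **Judgement:** the existing 5% and 10% limits, reported with an interval that allows for pitches clustered within athlete.
- **Other outcomes:** detection sensitivity and specificity against 95% as a secondary endpoint, and all other biomechanical variables labelled descriptive.
- **Consistency:** align section 2.1 and the abstract with the new endpoint. Confirm that device and markers record the same movements, since section 3.1.3 can be read as placing the markers only on the movements after the simulated game.

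The change uses data and limits already in the protocol and needs no further subjects. It costs an amendment and some added analysis specification. One variable must be chosen in advance, the endpoint can fail, and error estimated in unseen athletes may look worse than error from pooled pitches.
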